#### Study Follow-up and Discontinuation:

Subjects who discontinue study drug without a taper, e.g., takes study drug for less than 2 hours or progresses to an IV anesthetic drug (a 3rd line treatment) for seizure suppression or discontinues the study medication due to safety reasons will continue in the study and still have the in-patient follow-up and the week 2, 3, and 4 follow-up visits/contacts.

Subjects who early terminate from the study, e.g., due to consent withdrawn, should have the early termination procedures completed when early termination is being considered and as close as possible to the end of the study drug administration.

All subjects, except those who are early terminated from the study, will have the in-patient follow-up day and the follow-up visits/contacts at Weeks 2, 3, and 4. If the subject remains hospitalized these visits will be done in person but if the subject has been discharged these contacts will be conducted via telephone call. Even if a subject has been discharged, efforts will be made to have the subject return so at least one of the visits will be conducted in-person. These visits will be conducted weekly, starting approximately  $7 \pm 3$  days after the in-patient follow-up day.

During these visits/calls, the site will follow-up on all serious adverse events (SAEs) and non-serious adverse events (AEs), AE resolution that occurs, and concomitant medications. In total, each subject will be followed for approximately 4 weeks.

#### **Inclusion and Exclusion Criteria:**

##### **Inclusion Criteria:**

1. Subject, subject's parent, guardian, or LAR must provide signature of informed consent, and, once capable (per the investigator's hospital guidelines), there must be documentation of consent/assent by the subject indicating the subject is aware of the investigational nature of the study, is able and willing to participate in the study, and is aware of the required restrictions and procedures
2. Male or female subjects 12 years of age and older at the time of the first dose of study drug
3. Clinical and/or electrographic seizures defined as:
  - o Documented clinical seizures (convulsive SE): greater than 5 minutes' duration prior to treatment with study drug (per International League Against Epilepsy, ILAE)
  - or

- Electrographic criteria (one must apply):
  - 10 minutes of continuous seizure activity on EEG (per ILAE)
  - Intermittent EEG seizure activity for more than 50% of the previous 60 minutes
  - If less than 60 minutes of EEG is available, then intermittent electrographic seizure activity must be present for greater than 50% of the available duration of the EEG AND the electrographic seizure activity must be at least 10 minutes when taken in aggregate
- 4. Subject on concurrent 2nd line IV AED therapy with fosphenytoin/phenytoin, valproic acid, levetiracetam, lacosamide, or brivaracetam for the management of the current episode of SE
- 5. BMI < 40 or, if not able to be calculated at screening, assessed by investigator as not morbidly obese

**Exclusion Criteria:**

1. Life expectancy of less than 24 hours
2. Anoxic brain injury as the primary cause of SE
3. Recent (< 24 hour) traumatic brain injury as the primary cause of SE
4. Administered anesthesia (3rd line treatment, e.g., midazolam, propofol, thiopental, pentobarbital, or ketamine) at adequate doses and duration for the treatment of the current episode of SE that required the subject to be hospitalized and 5 half-lives of the agent used has not elapsed
5. Subjects who are intubated for the administration of an IV anesthetic drug (a 3rd line treatment; e.g., midazolam, propofol, thiopental, pentobarbital, or ketamine) to treat SE; subjects who are intubated for airway protection are not excluded
6. Subjects known or suspected to be pregnant upon screening
7. To the best knowledge of the investigator, has allergy to progesterone or allopregnanolone medications/supplements or has previously received ganaxolone or exogenous allopregnanolone
8. If renal impairment is suspected (eGFR < 45 mL/min) or subject is currently on dialysis; if decision is made to start dialysis during study participation, subjects are not excluded
9. To the best knowledge of the investigator, subject has hepatic insufficiency at screening, for example alanine transferase or aspartate transferase level more than 5 times the upper limit of normal (ULN), or total bilirubin more than 2 times ULN at the screening visit
10. Subjects with a durable medical care agreement that would not allow hospital to administer their standard of care for treatment of SE
11. Subjects on an investigational drug that is not recommended by treatment guidelines are required to have a reasonable expectation that the investigational study drug has been cleared from their system, that is, that five half-lives have elapsed
12. Subjects who have a history or evidence of a medical condition that, in the investigator's judgment, would expose subject to an undue risk of a significant adverse event or interfere with assessments of safety or efficacy during the course of the study

### **Maximum Duration of Subject Involvement in the Study:**

- Screening could be as short as a few minutes and as long as approximately 24 hours prior to the initiation of study drug. The screening period is from the time parent/guardian/LAR consent/assent is obtained to immediately prior to study drug initiation.
- The planned duration of adjunctive treatment is 2 days which includes a 12-hour study drug taper.
- There will be an in-patient follow-up period after the study drug administration is completed. The in-patient follow-up period starts at the time of study drug discontinuation; either at the end of the taper or if the study drug administration is stopped without a taper. The follow-up period consists of a 24 hour in-patient follow-up day and 3 weekly visits. These weekly visits can be performed as an in-person visit if the subject is still in the hospital, or as a telephone call if the subject has been discharged. However, it is recommended that discharged subjects return so at least one of these visits will be conducted in-person.
- In total, subjects will be followed for approximately 4 weeks.

### **Endpoints and Statistical Analysis:**

#### **Primary Endpoint:**

- The number of subjects who didn't require an IV anesthetic drug (a 3rd line treatment) for SE treatment within the first 24 hours after study drug initiation

#### **Secondary Endpoints:**

- For subjects on concomitant second-line therapy: time to cessation of SE or next treatment decision (defined as the need for an IV anesthetic drug (a 3rd line treatment) when on ganaxolone)
- Level of responsiveness as assessed by the GCS, Four Score Scale, and RASS at 24 hours post study drug initiation
- The number of subjects who did not require additional 2nd line IV AED therapy for SE treatment in the 24-hours after study drug taper
- Safety and tolerability of IV ganaxolone as adjunctive SE therapy as assessed by neurologic, EEG, physical examinations, clinical laboratory tests, ECGs, vital signs, and AEs
- Number of subjects who maintained SE resolution 24 hours after study drug taper and at Week 4
- Number of subjects with seizure(s) following the cessation of SE through the in-patient follow-up day
- Seizure burden assessed as duration of electrographic seizure activity per hour of EEG recording collected
- Clinical outcome as assessed by MRS at the in-patient follow-up day and Week 4
- Characterization of the pharmacokinetic profile of ganaxolone IV solution in SE subjects
- Length of stay in intensive care unit and hospital, mortality, morbidity, need for and duration of intubation and mechanical ventilation, and seizure freedom

## STUDY SCHEDULE(S)

**Table 1: Schedule of Assessments**

Periods	Screening a	Treatment			Follow-up b		ET	
Visit/Timepoint or Duration	Prior to study drug initiation	Dosing		Taper	Study Drug Discontinuation without Taper	In-patient Follow-up	Weekly follow-up (Week 2, 3, & 4)	Early Termination
	Day -1 to Day 1 Pre-dose through screening	Day 1 Study Drug Initiation 0 hours through 24 hours post study drug initiation	Day 2 24 hours through 36 hours post study drug initiation	Day 2 12-hours Starts at 36-hours post study drug initiation	Collected prior to or as close to study drug discontinuation as possible	Day 3 Or Starts as soon as study drug administration ends, lasts 24 hours	7 ±3, 14 ±3, and 21 ±3 days post last visit	Collected prior to or as close to study drug discontinuation as possible
Informed consent/assent	✓							
Inclusion/exclusion criteria	✓							
Demography and medical/ medication history c	✓							
Physical exam d	✓		✓		✓	✓		✓
Status Epilepticus Severity Score (STESS)	✓							
Vital signs e	✓	✓	✓	✓	✓	✓		✓
Glasgow Coma Scale (GCS)/Pediatric GCS (PGCS) e	✓	✓	✓	✓	✓	✓		✓
Richmond Agitation and	✓	✓	✓	✓	✓	✓		✓

**Table 1: Schedule of Assessments**

Periods	Screening a	Treatment			Follow-up b		ET	
Visit/Timepoint or Duration	Prior to study drug initiation	Dosing		Taper	Study Drug Discontinuation without Taper	In-patient Follow-up	Weekly follow-up (Week 2, 3, & 4)	Early Termination
	Day -1 to Day 1 Pre-dose through screening	Day 1 Study Drug Initiation 0 hours through 24 hours post study drug initiation	Day 2 24 hours through 36 hours post study drug initiation	Day 2 12-hours Starts at 36-hours post study drug initiation	Collected prior to or as close to study drug discontinuation as possible	Day 3 Or Starts as soon as study drug administration ends, lasts 24 hours	7 ±3, 14 ±3, and 21 ±3 days post last visit	Collected prior to or as close to study drug discontinuation as possible
Severity Scale (RASS) c								
Full Outline of UnResponsiveness (FOUR) Score c	✓	✓	✓	✓	✓	✓		✓
Mini mental state exam (MMSE) f				✓		✓		
12-lead ECG g	✓	✓		✓	✓	✓		✓
Biochemistry, hematology, and antiepileptic drugs h	✓	✓	✓	✓	✓	✓	✓	✓
Urinalysis h	✓	✓	✓	✓	✓	✓	✓	✓
Drugs of abuse, including alcohol i	✓							
Pregnancy test (WCBP only) i	✓							
EEG j	✓	✓	✓	✓	✓	✓		✓

**Table 1: Schedule of Assessments**

Periods	Screening a	Treatment			Follow-up b		ET	
Visit/Timepoint or Duration	Prior to study drug initiation	Dosing		Taper	Study Drug Discontinuation without Taper	In-patient Follow-up	Weekly follow-up (Week 2, 3, & 4)	Early Termination
	Day -1 to Day 1 Pre-dose through screening	Day 1 Study Drug Initiation 0 hours through 24 hours post study drug initiation	Day 2 24 hours through 36 hours post study drug initiation	Day 2 12-hours Starts at 36-hours post study drug initiation	Collected prior to or as close to study drug discontinuation as possible	Day 3 Or Starts as soon as study drug administration ends, lasts 24 hours	7 ±3, 14 ±3, and 21 ±3 days post last visit	Collected prior to or as close to study drug discontinuation as possible
Study Drug infusion k		✓	✓	✓				
Pharmacokinetic blood sampling l		✓	✓	✓	✓	✓		
Neurosteroid levels m	✓	✓						
Blood Gas n	✓							
Cerebral Spinal Fluid o	✓							
Clinical Global Impression of Severity (CGI-S) p	✓		✓	✓	✓	✓	✓	✓
Clinical Global Impression of Improvement (CGI-I) q		✓	✓	✓	✓	✓	✓	✓
SE & Seizure Questions r		✓	✓	✓	✓	✓	✓	✓
Intubation Question s		✓	✓	✓	✓	✓		
Modified Rankin Scale (MRS) t				✓	✓	✓	✓	✓

**Table 1: Schedule of Assessments**

Periods	Screening a	Treatment			Follow-up b		ET	
Visit/Timepoint or Duration	Prior to study drug initiation	Dosing		Taper	Study Drug Discontinuation without Taper	In-patient Follow-up	Weekly follow-up (Week 2, 3, & 4)	Early Termination
	Day -1 to Day 1 Pre-dose through screening	Day 1 Study Drug Initiation 0 hours through 24 hours post study drug initiation	Day 2 24 hours through 36 hours post study drug initiation	Day 2 12-hours Starts at 36-hours post study drug initiation	Collected prior to or as close to study drug discontinuation as possible	Day 3 Or Starts as soon as study drug administration ends, lasts 24 hours	7 ±3, 14 ±3, and 21 ±3 days post last visit	Collected prior to or as close to study drug discontinuation as possible
AEs/SAEs u		✓	✓	✓	✓	✓	✓	✓
Concomitant medication u	✓	✓	✓	✓	✓	✓	✓	✓

ET, Early Termination; ECG, electrocardiogram; WCBP, women of childbearing potential; EEG, electroencephalograms; AE, adverse event; SAE, serious AE.

a. The screening period is from the time parent/guardian/LAR consent is obtained to immediately prior to study drug initiation.

b. The planned duration of follow-up will be 24 hours after study drug administration is stopped (called the in-patient follow-up day) and weekly for an additional 3 weeks. For Weeks 2, 3, and 4 the follow-up can be performed as an in-patient visit if the subject is still in the hospital or, if the subject has been discharged, as a telephone call. Attempts should be made to have discharged subjects return for one of the follow-up visits for clinical laboratory sample collection. The follow-up visit window is 7 ±3, 14 ±3, and 21 ±3 days.

c. Demography and medical history will ideally be collected prior to study drug initiation but can be collected whenever feasible before the end of study drug taper.

d. Physical exam should be obtained from the subject's chart or completed pre-dose (screening) or, if not available, collected within 2-hours of study drug initiation, and at 36-hours (+/- 1-hour). Collect at the time of study drug discontinuation, either at the end of the study drug taper or if the study drug administration is stopped without a taper and 24-hours (+/- 1-hour) after study drug discontinuation. If possible, for subjects who early terminate from the study, collect at the time of early termination is being considered and as close as possible to the end of the study drug administration. Collect any time, if medically indicated, per investigator's judgment.

e. Vital signs including blood pressure, pulse, respiratory rate, temperature, and oxygen saturation and the GCS/PGCS, RASS, and the FOUR scales should be collected pre-dose (screening), 60-minutes (+/- 15-min) and 2- (+/- 15-min), 10-, 24-, and 36-hours (+/- 1-hour) after study drug initiation. Collect at the time of study drug discontinuation, either at the end of the study drug taper or if the study drug administration is stopped without a taper and 24-hours (+/- 1-hour) after study drug discontinuation. If possible, for subjects who early terminate from the study, collect at the time early termination is being considered and as close as possible to the end of the study drug administration. Collect any time, if medically indicated, per investigator's judgment. Weight and height should be collected pre-dose (screening) for calculation of BMI inclusion criterion, if feasible. If not collected pre-dose (screening) collect prior to the end of the in-patient follow-up day.

f. MMSE should be performed at the time consent/assent is administered to the subject for continued participation and then on the in-patient follow-up day. If the MMSE is not able to be assessed due to the subject's state this should be recorded.

g. ECG should be collected pre-dose (screening), 2- (+/- 30-min) and 36-hours (+/- 1-hour) after study drug initiation. Collect at the time of study drug discontinuation, either at the end of the study drug taper or if the study drug administration is stopped without a taper and 24-hours (+/- 1-hour) after study drug discontinuation. If possible, for subjects

**Table 1: Schedule of Assessments**

Periods	Screening a	Treatment			Follow-up b		ET	
Visit/Timepoint or Duration	Prior to study drug initiation	Dosing		Taper	Study Drug Discontinuation without Taper	In-patient Follow-up	Weekly follow-up (Week 2, 3, & 4)	Early Termination
	Day -1 to Day 1 Pre-dose through screening	Day 1 Study Drug Initiation 0 hours through 24 hours post study drug initiation	Day 2 24 hours through 36 hours post study drug initiation	Day 2 12-hours Starts at 36-hours post study drug initiation	Collected prior to or as close to study drug discontinuation as possible	Day 3 Or Starts as soon as study drug administration ends, lasts 24 hours	7 ±3, 14 ±3, and 21 ±3 days post last visit	Collected prior to or as close to study drug discontinuation as possible

who early terminate from the study, collect at the time early termination is being considered and as close as possible to the end of the study drug administration. Collect any time, if medically indicated, per investigator's judgment.

h. Clinical labs, hematology, serum chemistry (including creatinine, blood urea nitrogen, and estimated glomerular filtration rate calculation) and concomitant AED levels (fosphenytoin/phenytoin, valproic acid, levetiracetam, lacosamide, or brivaracetam, if available) and Urinalysis (including urine protein, albumin, and microscopic examination) should be collected pre-dose (screening), if available, or within 2 hours of study drug initiation, at 24- and 36- hours (+/- 1-hour) after study drug initiation. Collect at the time of study drug discontinuation, either at the end of the study drug taper or if the study drug administration is stopped without a taper and 24-hours (+/- 1-hour) after study drug discontinuation. Collect at one of the weekly follow-up visits (week 2, 3, or 4) for subjects in-house and if possible, for subjects who have been discharged. If possible, for subjects who early terminate from the study, collect at the time early termination is being considered and as close as possible to the end of the study drug administration. After the initial SE cessation, AED levels should be collected at time of first instance of seizure activity or SE relapse. Between study drug initiation and the in-patient follow-up day, where possible, collect AED levels if the decision is made to intubate the subject and for any serious adverse event (related or not related). Collect clinical labs, AEDs and urinalysis any time, if medically indicated, per investigator's judgment.

i. Drugs of abuse (urine or serum), including alcohol testing, and pregnancy test (urine or serum) for women who are of childbearing potential, should be collected pre-dose (screening). If not possible to collect pre-dose, collect as soon as possible after start of study drug infusion. Enrollment is not contingent upon results. However, if a subject has a positive test result, it will be at the investigator's discretion to weigh the risks versus benefits for the subject's continued participation. If the investigator decides to discontinue the study drug, refer to the study drug taper directions in the Study drug, Dose and Mode of Administration section.

j. EEG is required for confirmation of NCSE diagnosis. Continuous EEG recording ideally should start before study drug initiation and continue through the in-patient follow-up day. If continuous EEG is not possible or needed to diagnose (for convulsive SE) it should be instituted at the earliest possible time after study drug initiation (if a pre-dose EEG was not performed for the diagnosis of convulsive SE).

k. Subjects will receive a 30 mg bolus (over ~3 minutes) with a continuous infusion at a rate of 20-80 mg/hour for approximately 36 hours followed by 12-hour taper.

l. Blood sample collection for pharmacokinetic analysis (venous or arterial) will occur at 60-minutes then at 2-,4-,8-,10-, 24- and 36-hours after the start of study drug infusion. Collect at the time of study drug discontinuation, either at the end of the study drug taper or if the study drug administration is stopped without a taper and 24-hours after study drug discontinuation. After the initial SE cessation, collect a sample at the first instance of seizure activity or SE relapse and the subject does not progress to an IV anesthetic. Between study drug initiation and the in-patient follow-up day, where possible, collect a sample if the decision is made to intubate the subject; collect at the time of introduction of a new IV AED for safety/efficacy (not for AEDs given prophylactically for "transition/bridging"), and at the time of any serious adverse event (related or not related). PK samples cannot be collected from the study drug infusion line. The location of study drug access and location of PK sample collection should be documented in the subject's source.

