### **6.2.3 Dosing**

Total adjunctive ganaxolone IV solution therapy infusion treatment is planned to be 2 days which includes a 12-hour study drug taper. All subjects will have an ~3-minute bolus dose with a continuous infusion at the rate of 20-80 mg/hour, and a 12-hour study drug taper (see Table 2 and 3 for details). Once study drug administration is started it should be delivered for 2 days (48 hours) which includes a 12-hour taper.

Study drug should be administered, ideally, through a dedicated (peripheral or central) IV line. These infusion parameters result in daily doses of ganaxolone of  $\leq$  830 mg/day and Captisol of  $\leq$  50 g/day as agreed upon with the FDA. Based on PK modeling, it is predicted that maximum concentrations of ganaxolone should remain within 1,000 ng/mL during infusion, but some variability is expected due to, for example, differences in subjects' weight. Note, at any time, the infusion rate of the ongoing administration may be decreased for safety reasons, see Dose Adjustments and Interruptions section below for more information.

Note, pharmacokinetic data from study 1042-0405 in healthy volunteers showed that a bolus infusion of 30 mg ganaxolone over 5 minutes led to transient peak concentration levels ( $C_{max}$ ) above 1,000 ng/mL (maximal observed  $C_{max}$  was 1,850 ng/mL) with no safety concerns. Infusion of 30 mg/hour for 1 hour and 20 mg/hour for 4 hours led to concentrations of 258 and 215 ng/mL, respectively, again without any safety concerns (see Section 1.2 Product Background and Clinical Information).

During the open-label group, based on the safety, efficacy, and pharmacokinetic data from the ongoing study, the infusion parameters in subsequent subjects may be adjusted to maximize the safety and efficacy of study subjects. If the infusion parameters are amended, the new infusion parameters will not exceed the daily limit of 50 g/day Captisol ( $\leq$  830 mg/day ganaxolone) as agreed upon with the FDA. The revised infusion parameters will be communicated to Clinical Sites in a Protocol Administrative Change Memo and kept in the study and site files.

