**Table 2: Dosing for Subjects  $\geq 40$  kg (on an mg/hour basis)**

Days	Start Time from Study Drug Initiation	Study Drug Dose (mg/hour)	Study Drug Infusion Rate (mL/hour)	Duration
Day 1	0 hours: bolus dose via syringe or infusion pump	30	30	3 minutes
Day 1	0 hours through 2 hours post study drug initiation: continuous infusion, started with bolus	80	80	2 hours
Day 1	2 hours through 12 hours post study drug initiation	40	40	10 hours
Day 1	12 hours through 24 hours post study drug initiation	20	20	12 hours
Day 2 a	24 hours through 36 hours post study drug initiation	20 - 45	20 - 45	12 hours
Study Drug Taper				
Day 2 b	36 through 48 hours post study drug initiation (12-hour taper)	13.34 - 30.02	13.34 - 30.02	4 hours
		8.90 - 20.02	8.90 - 20.02	4 hours
		5.93 - 13.35	5.93 - 13.35	4 hours

a. On Day 2 (24-36 hours), the continuous infusion rate can be increased from 20 mg/hour to a maximum rate of 45 mg/hour at any time, if needed, to manage seizure relapse or other medical reason.

b. To taper the study drug, the infusion rate at the 36-hour post study drug initiation timepoint will be reduced by 33.3% every 4 hours until the infusion rate is stopped or if the infusion rate becomes too low to sustain the infusion line, at which point it will be stopped. The first taper will be 33.3% from the current infusion rate, the second taper will be 33.3% from the first tapered infusion rate, and the final taper will be 33.3% from the previous tapered infusion rate. If, per the investigator's judgment, the study drug taper needs to start at an earlier timepoint during the treatment period, the infusion rate at the start of the first taper will be decreased by 33.3% every 4 hours as described.

Subjects weighing  $< 40$  kg will be dosed on a per-kilogram basis:

- A 0.43-mg/kg bolus dose (over ~3 minutes) will be administered with a continuous infusion at a dose of 1.14 mg/kg/hour for 2 hours followed by a continuous infusion rate of 0.57 mg/kg/hour for 10 hours, and 0.29 mg/kg/hour for the remaining 12 hours of Day 1.
- On Day 2 (24-36 hours) the continuous infusion dose of 0.29 mg/kg/hour will continue until the start of the study drug taper at 36 hours post study drug initiation. If needed, to manage seizure relapse or for another medical reason, the infusion dose can be increased from 0.29 mg/kg/hour up to a maximum of 0.64 mg/kg/hour at any time during hours 24-36 of Day 2.

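### Table 1 footnote k states a 30 mg bolus and 20-80 mg/hour with no weight limit, which contradicts the per-kilogram regimen for every subject under 40 kg

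*Protocol*

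**What the plan says.** Footnote k of Table 1 (Schedule of Assessments) describes the infusion for subjects in general: "Subjects will receive a 30 mg bolus (over ~3 minutes) with a continuous infusion at a rate of 20-80 mg/hour", continuing for about 36 hours before a 12-hour taper. It names no weight group and does not mention Tables 2 and 3.

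Section 6.2.3 opens with a general sentence, "All subjects will have an ~3-minute bolus dose with a continuous infusion at the rate of 20-80 mg/hour, and a 12-hour study drug taper", and closes it with a pointer in brackets: "see Table 2 and 3 for details". This sentence gives a rate range but no bolus amount. The Synopsis and Section 7.1.2.1 repeat the same rate range without a weight limit.

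Section 6.2.3 then splits by weight, as does the Synopsis. From 40 kg upward (Table 2) the bolus is 30 mg, followed by 80, 40 and 20 mg/hour over Day 1. Below that, "Subjects weighing $< 40$ kg will be dosed on a per-kilogram basis". For this group: "A 0.43-mg/kg bolus dose (over ~3 minutes) will be administered with a continuous infusion at a dose of 1.14 mg/kg/hour for 2 hours", then "0.57 mg/kg/hour for 10 hours, and 0.29 mg/kg/hour for the remaining 12 hours of Day 1". Table 3 repeats these values and allows 0.29 to 0.64 mg/kg/hour in hours 24 to 36.

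**The concern.** The figures in footnote k match only the regimen for subjects of 40 kg or more, yet the footnote is not restricted to them. Lighter subjects can enter: Section 4.1 sets a minimum age of 12 and an upper BMI limit but no minimum weight, and Section 7.2.4.4 (Table 5) plans blood volumes for pediatric hospitals. For such a subject the Protocol states two different boluses and two different sets of rates.

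The Protocol's dose rules assume one specification. Rates may not be rounded up, increases above those the Protocol specifies are not allowed (Section 6.2.3), and overdose is defined against a prespecified daily total (Section 8.1.7). With two specifications for one subject, these rules have no single reference point. Treatment starts in an emergency, so a conflict in the stated bolus is a patient-safety matter.

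**Working it through.** **Inputs**
- Footnote k: bolus 30 mg; rate 20 to 80 mg/h.
- Section 6.2.3 and Table 2, 40 kg or more: bolus 30 mg; 80 mg/h for 2 h, 40 mg/h for 10 h, 20 mg/h for 12 h.
- Section 6.2.3 and Table 3, under 40 kg: bolus 0.43 mg/kg; 1.14 mg/kg/h for 2 h, 0.57 mg/kg/h for 10 h, 0.29 mg/kg/h for 12 h; up to 0.64 mg/kg/h in hours 24 to 36.
- Section 6.1: 59.74 mg Captisol per mg ganaxolone (both per mL of solution).

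**Reproducing the Protocol's own figure.** Day 1 at 40 kg or more is 30 + 80×2 + 40×10 + 20×12 = 30 + 160 + 400 + 240 = 830 mg. Captisol is 830 × 59.74 / 1000 = 49.6 g. Both agree with the stated limits of 830 mg/day and 50 g/day, so the regimen has been read as intended.

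**Table 3 in mg and mg/h (per-kilogram value × weight).** The 40 kg row is the bound that no subject in this group reaches.

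| Weight | Bolus (mg) | 0-2 h (mg/h) | 2-12 h (mg/h) | 12-24 h (mg/h) |
|---|---|---|---|---|
| 30 kg | 12.9 | 34.2 | 17.1 | 8.7 |
| 35 kg | 15.05 | 39.9 | 19.95 | 10.15 |
| 39.9 kg | 17.2 | 45.5 | 22.7 | 11.6 |
| 40 kg (bound) | 17.2 | 45.6 | 22.8 | 11.6 |
| Footnote k | 30 | 20-80 | 20-80 | 20-80 |

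**Where the two could agree**
- Bolus: 30 / 0.43 = 69.8 kg.
- Hours 12 to 24, at the 20 mg/h floor: 20 / 0.29 = 69.0 kg.

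Both weights are far above 40 kg, so the bolus and the 12-24 h rate conflict at every weight in the group. At 30 kg the bolus ratio is 30 / 12.9 = 2.3.

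**Phases that do not always conflict**
- 0-2 h reaches 20 mg/h at 20 / 1.14 = 17.5 kg and stays below 80 mg/h throughout the group.
- 2-12 h reaches 20 mg/h at 20 / 0.57 = 35.1 kg.
- In hours 24 to 36 the starting rate is below 11.6 mg/h; only the permitted maximum can enter the range, from 20 / 0.64 = 31.25 kg.

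**Day 1 totals**
- Table 3: 0.43 + 1.14×2 + 0.57×10 + 0.29×12 = 11.89 mg/kg. This is 356.7 mg at 30 kg and below 11.89 × 40 = 475.6 mg for anyone in the group.
- Footnote k, at its lowest rate throughout: 30 + 20×24 = 510 mg.

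The lowest Day 1 total that footnote k permits is above the highest that Table 3 permits.

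**The case against.** The strongest reply is that footnote k is a summary line that leaves out the lighter weight group. The Protocol says explicitly that subjects under 40 kg are dosed per kilogram and gives them their own table. Sites are sent to the Pharmacy Manual for dosing by the Synopsis, Section 6.2.3, Table 3 and the vial label. Nothing in the documents calls Table 1 a dosing reference. A range of 20 to 80 mg/hour might also be read loosely.

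Much of this stands. It limits the point to a wording contradiction whose intent can be recovered elsewhere. It does not remove it: footnote k states a specific bolus, carries no pointer, and sits on the study drug infusion row of the table to which Section 7.1 sends sites for scheduled procedures. A loose reading of the range does not help either, as the Day 1 totals show.

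Three stronger readings are tempting, and the documents do not support them.
- A reader might infer that Section 6.2.3, the Synopsis and Section 7.1.2.1 are equally at fault. Their rate range is inconsistent with Table 3, but the opening sentence of 6.2.3 gives no bolus amount and cites Tables 2 and 3, the Synopsis goes straight on to separate regimens by weight, and 7.1.2.1 refers to Section 6.
- A reader might set the first-phase rate, such as 34.2 mg/h at 30 kg, against 80 mg/h. That treats the top of a range as a required rate; 34.2 mg/h lies inside it.
- A reader might infer that the exposure summaries are affected. SAP Section 4.9.7 lists and summarises drug actually administered, SAP Section 1 defines the cohorts by target mg/day, and the SAP rests on Amendment 3, whose schedule footnote has a 25 mg bolus and 18-80 mg/hour. No planned analysis uses the current footnote k.

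**Conclusion.** The contradiction is real and is located in footnote k: its text and the per-kilogram regimen cannot both be followed for any subject under 40 kg. Two elements conflict throughout that group, the bolus and the rate in hours 12 to 24. The other phases conflict only at some weights.

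The comparison of Day 1 totals assumes an uninterrupted infusion without rate reductions. The documents do not say how many subjects weigh under 40 kg, so the number affected is unknown. They also do not show that any subject was dosed from the footnote. The point is wrong as written: modest in extent, but more than a typographical matter because it concerns a stated dose. No view is taken on which dose is right.

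**What to change.** Reconcile footnote k with the weight-specific dosing text in the Synopsis, Section 6.2.3 and Table 3, either by qualifying it by weight or by replacing the figures with a reference to Tables 2 and 3. Align the general 20-80 mg/hour sentences in the Synopsis, Section 6.2.3 and Section 7.1.2.1 in the same edit. The note under Figure 1 also gives mg/hour rates for hours 24 to 36 without a weight limit and can be checked then. The sponsor must confirm the intended regimen; none is proposed here.

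The cost is protocol wording only. Sample size, endpoints and planned analyses do not change.
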